4.4 Permissible and Prohibited Medications/Treatments

4.4.1 Permissible Medications/Treatments

Medications which are not specifically prohibited in Section 4.4.2 are allowed, with the following clarifications and restrictions:

The following medications for the acute treatment of migraine are allowed during the study:

- any triptan
- any ergot derivative
- any opioid
- any other form of analgesic (including acetaminophen)
- any NSAID agent
- any antiemetic agent

Aspirin up to 325 mg/day is allowed for cardiac prophylaxis.

Selective serotonin reuptake inhibitors (SSRI) or serotonin norepinephrine reuptake inhibitors (SNRI) will be permitted provided that treatment is stable for at least 60 days prior to screening (Visit 1) and continues without change in dose throughout the study.

Therapy considered necessary for the patient's welfare may be given at the discretion of the investigator. If the permissibility of a specific medication/treatment is in question, please contact Allergan.

4.4.2 Prohibited Medications/Treatments

The following medications are prohibited 30 days prior to Visit 1(unless otherwise indicated) and throughout the study period:

- Strong and moderate cytochrome P450 3A4 (CYP3A4) inhibitors, including but not limited to: systemic (oral/intravenous [IV]) itraconazole, ketoconazole, fluconazole; erythromycin, clarithromycin, telithromycin; diltiazem, verapamil; aprepitant, cyclosporine, nefazodone, cimetidine, quinine, and HIV protease inhibitors
- Strong and moderate CYP3A4 inducers, including but not limited to: barbiturates (eg, phenobarbital and primidone), systemic (oral/IV) glucocorticoids, nevirapine, efavirenz, pioglitazone, carbamazepine, phenytoin, rifampin, rifabutin, and St. John's wort
- Strong organic anion transporting polypeptide 1B1 (OATP1B1) inhibitors (eg, gemfibrozil)
- Drugs with narrow therapeutic margins with theoretical potential for CYP drug interactions (eg, warfarin)
- Medications with demonstrated efficacy for the prevention of migraine (eg, amitriptyline, topiramate, propranolol). Refer to Section [12.3](#).
- Botulinum toxin injections (eg, Botox[®]) into areas of the head, face, or neck within 6 months prior to Visit 1 and throughout the study period
- Acupuncture, TENS (transcutaneous electrical nerve stimulation), cranial traction, nociceptive trigeminal inhibition or occipital nerve block treatments, or dental splints for headache, within 4 weeks prior to entry into the baseline phase at week -4 or at any time during the study (including the week -4 to day 1 baseline phase)

The decision to administer a prohibited medication/treatment is done with the safety of the study participant as the primary consideration. When possible, Allergan should be notified before the prohibited medication/treatment is administered.

4.4.3 Definition of Females of (Non-)Childbearing Potential and/or Acceptable Contraceptive Methods

For purposes of this study, females will be considered of childbearing potential unless they are naturally postmenopausal (ie, no menses for 2 years) or permanently sterilized (ie, bilateral tubal ligation, bilateral salpingectomy, bilateral oophorectomy, or hysterectomy).

For women of childbearing potential who may participate in the study, the following methods of contraception, if properly used, are generally considered reliable: hormonal contraceptives (ie, oral, patch, vaginal ring, injection, implant), male condom with intravaginal spermicide, diaphragm or cervical cap with spermicide, intrauterine device, vasectomized partner, or sexual abstinence.

For males who may participate in the study, the following methods of contraception, if properly used, are generally considered reliable: post-bilateral vasectomy, barrier contraception or sexual abstinence. Male participants must also refrain from donating sperm during the course of the study.

The investigator and each patient will determine the appropriate method of contraception for the patient during the participation in the study.

If a female becomes pregnant during the study, the investigator will notify Allergan immediately after the pregnancy is confirmed and the patient will be exited from the study after appropriate safety follow-up. The investigator will (1) notify the patient's physician that the patient was being treated with an investigational drug AGN-241689 and (2) follow the progress of the pregnancy. The investigator must document the outcome of the pregnancy and provide a copy of the documentation to Allergan.

4.4.4 Special Diet or Activities

Patients should refrain from consuming grapefruit or grapefruit juice from the time the consent form is signed until completion of the study. Patients should also refrain from making significant changes to their diet or caffeine intake during the study.

Alcohol intake should be limited to no more than 3 drinks per day throughout the study. A drink is defined as a 12-ounce can/bottle of beer, a 4-ounce glass of wine, or 1 ounce of liquor.

5. Study Treatments

5.1 Study Treatments and Formulations

Over-encapsulated tablets containing 10-mg [REDACTED], 30-mg [REDACTED] and 60-mg [REDACTED] of AGN-241689

5.2 Control Treatment(s)

Placebo [REDACTED] over-encapsulated tablets

5.3 Methods for Masking/Blinding

All study treatments will be provided in identical blister cards to maintain masking of the study.

Over-encapsulation will also be implemented to maintain study masking, and all patients will be instructed to take investigational product twice daily (one capsule in the morning and one capsule in the evening) at approximately the same times each day. Patients, therefore, will receive either placebo twice daily, a morning dose of AGN-241689 with an evening dose of placebo, or AGN-241689 twice daily.

5.4 Treatment Allocation Ratio and Stratification

Patients will be randomized to the following 6 arms in a 2:1:2:1:2:1 ratio:

- Placebo (n = 180)
- AGN-241689 10-mg QD (n = 90)
- AGN-241689 30-mg QD (n = 180)
- AGN-241689 30-mg BID (n = 90)
- AGN-241689 60-mg QD (n = 180)
- AGN-241689 60-mg BID (n = 90)

No stratification will be performed.

5.5 Method for Assignment to Treatment Groups/Randomization

Prior to initiation of study treatment, each patient who provides informed consent will be assigned a patient number that will serve as the patient identification number on all study documents.

Central implementation of by-site randomization will be used for this study to assign patients into treatment groups.

At the time of randomization (i.e., Visit 2), eligible patients will be randomized by blocks in a 2:1:2:1:2:1 ratio into the following arms: placebo, 10-mg AGN-241689 QD, 30-mg AGN-241689 QD, 30-mg AGN-241689 twice daily, 60-mg AGN-241689 QD, and 60-mg AGN-241689 twice daily.

An automated interactive web response system (IWRS) will be used to manage the randomization and treatment assignment based on a randomization scheme prepared by Allergan Biostatistics.

Investigational product will be labeled with medication kit numbers. The IWRS system will provide the site with the specific medication kit number(s) for each randomized patient at the time of randomization. Sites will dispense investigational product according to the IWRS instructions. Sites will also log onto the IWRS at subsequent visits to obtain a kit number for dispensing investigational product. Sites will receive the IWRS confirmation notifications for each transaction. All notifications are to be maintained with the study source documents.

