#### 5.1.1.3.1 Efficacy Endpoints

The efficacy endpoints are summarized in the table below. Analyses of HEOR endpoints (ACM-I total and domain scores, PGIC, WPAI-SHP V2.0, *patient satisfaction with study medication, HIT-6,* and EQ-5D-5L) will be specified in a separate HEOR SAP.

Table 5–14Efficacy Analysis

Endpoint	Description	Timing	Methodology
Endpoint 1	Change from baseline in mean monthly MPM	Treatment	CFB MMRM
P1	headache days across the 12-week treatment period	period	Sensitivity Analyses:
			• PMM
			Robust regression

Endpoint	Description	Timing	Methodology
			(Refer to Section 6.4.3 for details)
Endpoint 2 S1	Change from baseline in mean monthly headache days across the 12-week treatment period	Treatment Period	CFB MMRM
Endpoint 3 S2	Proportion of participants with at least a 50% reduction in mean monthly MPM headache days across the 12-week treatment period	Treatment Period	Responder GLMM
Endpoint 4 S3	Change from baseline in mean monthly acute medication use days across the 12-week treatment period	Treatment Period	CFB MMRM

¹ Analysis visits defined in Section 6.2.1.

MPM = migraine/probable migraine. CFB = change from baseline; MMRM = mixed model for repeated measures; GLMM = generalized linear mixed model.

P1: primary efficacy parameter; S1-S3: secondary efficacy parameters. Endpoint 5 - 12: additional efficacy parameters

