## 6.4.2 Primary Efficacy Analysis

The primary efficacy endpoint is the change from baseline in mean monthly MPM headache days across the 12-week treatment period. The endpoint will be analyzed using MMRM. The response variable is the change from baseline to each postbaseline month in monthly MPM headache days. The model will include baseline monthly MPM headache days as a covariate, treatment group and visit (month) as fixed factors, and treatment group-by-visit and baselineby-visit as interaction terms. The analysis will be performed based on evaluable postbaseline data using only the observed cases without imputation of missing values.

Restricted maximum likelihood method will be used. The within-patient correlation will be modeled using the unstructured covariance matrix. If the model does not converge, then the compound symmetry covariance structure will be used. The Kenward-Roger approximation will be used to estimate denominator degrees of freedom. Contrasts will be constructed to obtain the average treatment effects across the 12-week treatment period to compare each atogepant treatment group versus the placebo group. Each treatment effect and treatment comparisons will be estimated by the LS Means and their differences in LS Means, along with their SE and 95% confidence intervals, and the p-value corresponding to the betweentreatment group difference.

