#### 6.4.3 Sensitivity Analysis

#### 6.4.3.1 Pattern-Mixture Model

The sensitivity analysis will use a pattern-mixture model (PMM) approach based on the *reference-based* copy reference method (Carpenter et al, 2013) for missing value imputation. *This approach considers a missing-not-at-random (MNAR) mechanism for missing data and is to assess the impact of potential deviation of MAR assumption in the primary analysis.* 

Note that the missingness is assumed monotonic. Any intermediate missing values, if any, will be imputed at first. If the intermediate missing value exists at the first postbaseline month, it is imputed using the average of baseline and next available postbaseline values; otherwise, intermediate missing values are imputed using last observation carried forward (LOCF) approach.

The details of missing data imputation using the copy reference method are as follows:

- 1. The reference-based approach uses the placebo group as the reference. The missing values in the reference group are imputed using the observed data in that group under the missing-at-random assumption. The missing pattern is defined by the participant's last visit with a non-missing value. The mean vector and the covariance matrix of the multivariate normal distribution are estimated for reference group.
- 2. For atogepant treatment groups, missing values are imputed based on the distribution estimated from the reference group (from Step 1).
- 3. The MI (Step 1 and 2) will be performed 20 times and result in 20 imputed datasets. Each of the 20 imputed datasets will be analyzed using ANCOVA model. For a given imputed dataset, the average change from baseline in monthly MPM headache days is calculated across the 3 post-baseline months and is used as the response variable in the model. The model includes treatment group as a fixed factor and baseline monthly MPM headache days as a covariate. The LS mean difference and corresponding SE is estimated from the model comparing each atogepant treatment group with the placebo group.
- 4. The ANCOVA analysis results from 20 completed datasets are combined for overall estimation and inference using Rubin's rule (1987) to produce a pooled estimate of LS mean difference, its SE, and corresponding p-value for the test of null hypothesis of no treatment effect.

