#### 6.4.3.2 Robust Regression

The sensitivity analysis uses MI in conjunction with robust regression to assess the robustness of the primary MMRM analysis to the possible violation of normality assumption. This method has been described and referred as ADAP [R] in Mehrotra et al. 2012. The details of method are as follows.

The normality test is performed on the residuals which are generated by the same MMRM as used for the primary efficacy analysis. The residuals are scaled by the inverse Cholesky root of its estimated variance-covariance matrix. The Kolmogorov-Smirnov (K-S) test for normality is applied to the de-correlated and scaled residuals and normality test is rejected if p-value from the K-S test is less than 0.01.

If the normality test is rejected, sensitivity analysis below will be performed:

- 1. Create complete datasets using MI based on the Markov chain Monte Carlo (MCMC) approach. Imputed data will consist of 20 complete datasets.
- 2. Each of the 20 complete datasets will be analyzed using robust regression (Mestimation) to protect against either observed outliers in the original incomplete dataset, or imputed outliers in the completed datasets. For a given complete dataset, the average change from baseline in monthly MPM headache days is calculated across the 3 postbaseline months and is used as the response variable in the robust regression model. The model includes treatment group as a fixed factor and baseline monthly MPM headache days as a covariate. The mean difference and corresponding SE is estimated from the model comparing each atogepant treatment group with the placebo group.
- 3. The robust analysis results from 20 completed datasets are combined for overall estimation and inference using Rubin's rule (1987) to produce a pooled estimate of treatment difference, its SE, and corresponding p-value for the test of null hypothesis of no treatment effect.

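### Protocol 5.5 randomises by site in blocks, 5.4 and the synopsis say there is no stratification, and the primary model has no site term: clarify, and if blocks are held within site, adjust for it as a cheap gain in efficiency

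*Protocol*

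**What the plan says.** **Randomisation.** Protocol 5.5: "Central implementation of by-site randomization will be used for this study to assign patients into treatment groups". The same section says "eligible patients will be randomized by blocks in a 2:1:2:1:2:1 ratio into the following arms". It gives no block size and leaves the details to a scheme prepared by the sponsor's biostatistics group. Protocol 5.4 says "No stratification will be performed", and the synopsis says the same. Protocol 4.1 plans about 810 patients at about 75 sites, or 810/75 = 10.8 per site.

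**Primary model.** SAP 6.4.2: "The model will include baseline monthly MPM headache days as a covariate, treatment group and visit (month) as fixed factors", plus treatment-by-visit and baseline-by-visit interactions. Protocol 7.3.1 lists the same terms. Neither lists site. The covariance is unstructured, with one fallback: "If the model does not converge, then the compound symmetry covariance structure will be used".

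**Other models.**
- The responder GLMM (SAP Table 5-2), the copy-reference ANCOVA (SAP 6.4.3.1) and the robust regression (SAP 6.4.3.2) have no site term.
- The imputation steps do not mention site either: "The mean vector and the covariance matrix of the multivariate normal distribution are estimated for reference group" in the pattern-mixture analysis, and "Create complete datasets using MI based on the Markov chain Monte Carlo (MCMC) approach" in the robust one.
- The first secondary endpoint (S1), "Change from baseline in mean monthly headache days across the 12-week treatment period", and the third (S3), acute medication use days, are assigned to an MMRM of change from baseline. In the copy read here, the row of SAP Table 5-2 that defines this MMRM is incomplete. Protocol 7.3.2 says only that it is an MMRM with a baseline covariate.

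**The concern.** Blocks held within site make site a factor that the design balances. Balance removes most of the site effect from each treatment comparison, but a model without site still counts the between-site variance as residual error. The estimate is sound, its standard error is somewhat too large, and the test rejects a little less often than its nominal level. If blocks run centrally across sites, none of this follows.

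A reader cannot tell from the protocol which case applies. That decides whether the primary analysis reflects the randomisation in a trial intended to support registration. It is better settled before unblinding, because deciding afterwards whether to adjust for site would be open to the charge of being data-driven.

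**Working it through.** **Inputs from the documents.** Common SD 3.0. Placebo n = 180. Differences from placebo of 1.5 (60 mg QD, n = 180), 1.6 (60 mg BID, n = 90) and 1.2 (10 mg QD, n = 90) (Protocol 7.7, SAP 5.1.2). Tests are two-sided. Alpha of 0.025 goes to each of 60 mg QD and 60 mg BID (SAP 5.1.1.3.3).

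**Assumed, because the documents give no figure.** Blocks of 9, the smallest that fits 2:1:2:1:2:1. Site share ρ of the variance of the 12-week mean, after baseline, of 2, 5 or 10%. For the three-visit calculation, a between-visit correlation of 0.7 and dropout of 0 or 15%.

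**The plan's own figures.** With d = difference/(3·√(1/n + 1/180)) and power Φ(d − c):
- 60 mg QD: d = 4.743, c = 2.241, power 99.4% (stated 99.3%).
- 60 mg BID: d = 4.131, c = 2.241, power 97.1% (stated 97.0%).
- 10 mg QD: d = 1.2/(3·√(1/90 + 1/180)) = 3.098. At alpha 0.01 (c = 2.576) power is 69.9%. The stated 80.3% also reflects recycled alpha.

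Simulating the testing graph, with BID weights taken to mirror QD and secondary effects assumed at 0.8 times the primary, gave 97.0/91.3/99.4/97.7/80.1% for 60 BID, 30 BID, 60 QD, 30 QD and 10 QD. The stated figures are 97.0/91.4/99.3/98.1/80.3%. So the plan's power is reproduced without a site term.

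**Size of the test, perfect balance within site.** The true SE is √(1 − ρ) times the model SE, so the actual size is 2·(1 − Φ(2.241/√(1 − ρ))), which gives 0.0236/0.0215/0.0181 for ρ = 2/5/10%.

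**Size with incomplete blocks.** At about 10.8 patients per site the last block is usually cut short, so balance is imperfect. A three-visit generalised least squares calculation (75 sites, 810 patients, blocks of 9) gave:

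| Blocks | Dropout | Size at ρ = 2/5/10%, nominal 0.025 |
|---|---|---|
| Within site | 0 | 0.0238/0.0220/0.0191 |
| Within site | 15% | 0.0238/0.0220/0.0192 |
| Central | 0 | 0.0250/0.0250/0.0251 |

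With within-site blocks, the SEs without site are about 0.9/2.2/4.5–5% too wide. Simulation of the 12-week mean (4,000 trials per setting, similar/skewed site sizes) gave sizes of 0.0251/0.0232 at 2%, 0.0232/0.0221 at 5% and 0.0208/0.0198 at 10%. The Monte Carlo SE is about 0.002, so the 2% case cannot be told from nominal this way.

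**Power gained by a site term, within-site blocks.** Without site, power is Φ((d − c)/√(1 − ρ)); with site, Φ(d/√(1 − ρ) − c).
- 60 mg QD at 10%: 99.58 → 99.71, a gain of 0.13 points.
- 60 mg BID at 10%: 97.68 → 98.27, a gain of 0.59 points.
- 10 mg QD at c = 2.246, which gives the stated 80.3% when ρ = 0: 80.5 → 81.2, 80.9 → 82.5 and 81.6 → 84.6, or gains of about 0.6/1.5/3.1 points.

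The last set is the perfect-balance limit. Simulation at the same critical value gave 0.6/0.6, 1.5/1.8 and 2.4/2.8 points (similar/skewed sites). With no site variance, the site term cost no power.

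**The case against.** The strongest reply is that nothing in the plan fails. The statement that there is no stratification can mean no patient-level factors, which fits by-site blocks. The unseen randomisation scheme may already settle the matter. Leaving out a balanced factor makes a test conservative, which harms no claim of efficacy. Even without site, 10 mg QD power under within-site balance is 80.5 to 81.6% in the check above, not below the stated 80.3%. The effect disappears if blocks are central or sites do not differ. A site term also adds some convergence risk, and the primary model would then differ from its sensitivity analyses in covariates as well as in the assumption each is meant to probe.

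Most of this stands, and it keeps the point minor. A reader might infer that 5.4 and 5.5 flatly contradict each other; the documents support only an ambiguity. A reader might also infer that S1 and S3 certainly omit site; the incomplete table row does not allow that. What remains is that the protocol does not say how the blocks are held, and no reason is given for leaving out a factor by which patients are apparently randomised. The comparability objection is fair, and the fix meets it by also reporting the primary model without site.

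**Conclusion.** The concern holds as a minor point of clarity and efficiency, not as an error in the primary inference. If blocks are held within site and site explains 2 to 10% of the variance, a nominal 0.025 test runs at about 0.024 to 0.019. Forgone power is well under 1 point for the two arms that hold all the initial alpha. For 10 mg QD, which the SAP itself calls potentially sub-optimal, it is about 0.6/1.5/2.4–3.1 points.

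It would be tempting to read the missing site term as biasing the estimates, inflating false positives or leaving the trial short of its stated power. None of these follows: the direction is conservative and the stated powers are met without site.

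The sizes rest on an assumed site variance and block size. For 10 mg QD, a single critical value stands in for the full testing graph. Confidence is medium, because within-site blocking is the natural reading but is not confirmed.

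**What to change.** Before unblinding, state in Protocol 5.4, 5.5 and the synopsis whether blocks are held within site. The block size need not be disclosed to sites.

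**If blocks are held within site:**
- Add site as a random intercept to the primary MMRM, and to the S1 and S3 MMRMs if their full specification also lacks it. No pooling of small sites is needed.
- Fix the fallback order: if the model does not converge, drop the site term first, then apply the existing compound-symmetry fallback.
- Also report the primary MMRM without site. The pattern-mixture and robust-regression analyses, kept as written, can then be compared with a model using the same covariates.
- Keep the responder GLMM as written, because adding site to a logistic model changes the conditional odds ratio being estimated.
- Record the change in SAP 5.2.2.

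**If blocks are central:** correct the wording of 5.5 and leave the models unchanged.

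The cost is a clarifying sentence, one random term in up to three models, one fallback sentence, one SAP entry and one extra model run. The downside is a slight added risk of non-convergence.

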5.6 Treatment Regimen and Dosing

Treatments to be used in this trial are listed in ([Table 5–1](#)). Patients who meet all of the study entry criteria at Visit 2 will be randomized and provided with investigational product to be taken on an outpatient basis. Sites will subsequently dispense investigational product to patients at Visits 3, 4, 5, and 6. Patients will take their first dose of investigational product at the clinic at Visit 2 ([Section 8.5](#)) and will be instructed to take their investigational product twice daily (approximately 12 hours interval between doses) at approximately the same times each day. Investigational product will be administered orally for 12 weeks, and patients will be followed for 4 weeks following discontinuation of the investigational product.

Table 5–1 **Study Treatments**

Drug/Dose	Investigational Product Frequency	Investigational Product Administration (AM/PM)	Route of Administration
Placebo	Twice Daily	Placebo/ Placebo	Oral (capsule)
AGN-241689 10 mg QD	Twice Daily	AGN-241689 10 mg/ Placebo	Oral (capsule)
AGN-241689 30 mg QD	Twice Daily	AGN-241689 30 mg/ Placebo	Oral (capsule)
AGN-241689 30 mg BID	Twice Daily	AGN-241689 30 mg/ AGN-241689 30 mg	Oral (capsule)
AGN-241689 60 mg QD	Twice Daily	AGN-241689 60 mg/ Placebo	Oral (capsule)
AGN-241689 60 mg BID	Twice Daily	AGN-241689 60 mg/ AGN-241689 60 mg	Oral (capsule)

